1. 33% OAC initiation rate in the delayed intervention arm
2. 38% OAC initiation rate in the early intervention arm (5% absolute improvement in OAC initiation over the 33% OAC initiation expected in the delayed intervention arm over 1-year follow-up)
3. 1-year attrition rate: 30% dropout or lost-to-follow-up
4. Two-sided type I error rate of 0.05
5. Roughly 10,000 patients who meet the inclusion/exclusion criteria will yield more than 99% power to detect a 5% absolute difference

Power	Total sample size (2-arm)	Early Intervention	Delayed Intervention
90%	5610	2805	2805
95%	6910	3455	3455
99%	9718	4859	4859

2. Important Secondary Outcome of Stroke or TIA

A study with approximately 80,000 patients could provide reasonable power for stroke or TIA outcome under certain assumptions listed below:

- 1-year stroke or TIA rate: 18% among patients not treated with OAC
- 1-year stroke or TIA rate: 7% among patients treated with at least 1 OAC fill
- Duration of follow-up: 1 year
- 33% of delayed intervention patients will have at least 1 fill of OAC, meaning the 1-year stroke or TIA rate in the delayed intervention group would be 14.4%
- 1-year attrition rate: 30% dropout or lost-to-follow-up
- Two-sided type I error of 0.05
- If 38% of early intervention patients have at least 1 fill of OAC (meaning the 1-year stroke or TIA rate in the early intervention group would be 13.82%, i.e., an absolute reduction of 0.55%), the study will have 46% power to detect this 0.55% reduction. However, if 40.5% of early intervention patients have at least 1 fill of OAC (meaning the 1-year stroke or TIA rate in the

early intervention group would be 13.54%, i.e., an absolute reduction of 0.83%), the study will have 80% power to detect this 0.83% reduction.

8. The sample size has 80% power to detect a 0.5% absolute reduction in stroke, assuming a cumulative 1-year incidence of stroke of 4.2% in control (delayed intervention arm) patients and 3.7% in intervention (early intervention arm) patients. The assumption is that patients not on oral anticoagulation have an annual stroke rate of 5%, and stroke will be reduced by 50% (HR=0.5) in the treated (anticoagulated) population. The 80% power requires that 52% of early intervention arm patients are treated at 1-year as compared to 33% in the control arm.

II. STATISTICAL ANALYSIS

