All possible person-time will be used to assess participants’ outcomes. For the time-to-event analysis, patients will be censored from the analysis at the time of death, disenrollment from the health plan, loss of medical or pharmacy coverage, or change in eligibility for inclusion in research based on health plan membership.

[figure not shown]
Providers may have more than 1 patient in the study – either within the same arm or in both the early and delayed intervention arms. The frequency of this, when provider overlap can be identified, will be reported descriptively and it is expected to be a low proportion of whole population. Depending on the number of patients in this scenario, a sensitivity analysis may be considered to examine the effect.

There were a few variations in the implementation of the early intervention across the Data Partners due to pragmatic issues. The intervention per the protocol is targeted at both member and provider (i.e., the provider who gave most recent AF diagnosis). If the AF provider was a facility in the source data, the educational intervention was applied to the member only, unless the site chose an alternate provider. In the latter case, the intervention was sent to both the member and the alternate provider. The number of patients in each of these variations to the intended intervention will be reported.

A detailed Consort flow diagram will be provided showing the number of patients randomized to the early and delayed intervention groups, the numbers of subjects lost to follow up or excluded from analyses, and the number of subjects evaluable for the key study endpoints (Figure 1).¹

All analyses will be conducted using SAS version 9.4 or higher software (SAS Institute Inc., Cary, NC). However, version and modules to be used could vary from one Data Partner to another. All tests will be two-sided and a p-value of <0.05 will be considered statistically significant. No multiplicity adjustment will be made.

Figure 1. Consort Flow Diagram

A. METHODS FOR ANALYSIS IN DISTRIBUTED DATA NETWORKS

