Where $T = (p_{12}, p_{13}, \dots, p_{1k})'$, $p_{1k} = \Pr(\text{category } k \mid \text{early intervention})$, $k \in \{2, 3, \dots, k\}$,

$C = (p_{22}, p_{23}, \dots, p_{2k})'$, $p_{2k} = \Pr(\text{category } k \mid \text{delayed intervention})$, $k \in \{2, 3, \dots, k\}$,

S is a $(k - 1) \times (k - 1)$ covariance matrix define as:

$$S = [S_{kl}] = \begin{cases} \frac{[p_{1k}(1 - p_{1k}) + p_{2k}(1 - p_{2k})]}{2}, & k = l \\ \frac{[p_{1k}p_{1l} + p_{2k}p_{2l}]}{2}, & k \neq l \end{cases}$$

Aggregate standardized mean differences will be calculated based on aggregated frequencies, mean, and standard deviations.

Each Data Partner will run the SAS program(s) distributed by HPHCI, developed with the statistical team at Duke, to generate a summary table for their cohort of patients shown in example Tables 1 and 1S in Appendix A (there will be one for each Data Partner) and return the summary table to HPHCI. The same summary table will be generated for entire study population by HPHCI, as shown in Tables 1 and 1S in Appendix A.

As part of the provider intervention materials, providers had the opportunity to respond and provide an explanation for why their patients were not being treated with OAC. The data collected from these responses will be aggregated by rationale for non-treatment and reported as counts (percentages) by the coordinating center.

C. PRIMARY ENDPOINT DATA ANALYSES

The proportion of patients with evidence of at least one OAC medication fill over the course of the follow-up (through the date on which at least 80% of eligible study participants have at least 12 months of follow-up time) is the primary endpoint. The definition for OAC medication fill will be an OAC medication billing in the outpatient pharmacy claims, at least 4 INR tests or results in the laboratory claims (indicative of OAC use that was not billed through the pharmacy claims data), or a single procedure code that indicates use of anticoagulation. The primary endpoint will be summarized and compared between the early intervention and delayed intervention arms. Both unadjusted and adjusted

(based on available baseline risk factors) analyses will be conducted for the difference in the primary endpoint between the early intervention and delayed intervention arms using the data shown in Tables 2a-c. The adjusted analysis will be considered the primary analysis.

1. Adjusted Analysis Model

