The proportion of patients actively on OAC at the end of follow-up will be summarized and compared between the early intervention and delayed intervention arms. Last Observation Carried Forward will be used if the patient is censored. To evaluate whether the early patient-level and provider-level educational intervention increases the proportion of patients being actively on OAC at the end of follow-up, we will calculate the odds ratio (i.e., the odds of an average patient in the early intervention group being actively on OAC at the end of follow-up as compared to the odds of an average patient in the delayed intervention group being actively on OAC at the end of follow-up) using logistic regression model adjusted for baseline risk factors listed in Appendix A Table A, with GEE to account for the correlation of responses among the patients from a same service provider. The odds ratio, 95% confidence interval (CI) and p-value will be presented to show whether there is a statistically significant difference in the proportion of patients who are actively on OAC at the end of follow-up between the early intervention and delayed intervention groups. Each Data Partner will run the SAS program(s) distributed by HPHCI, developed with the statistical team at Duke DCC, to perform logistic regression analysis on their cohort of patients and return the parameter estimate (SE), estimated odds ratio, 95% confidence interval (CI) and p-value, shown in Table 6 in Appendix A (there will be one for each Data Partner), to HPHCI. Meta-analysis methods with inverse-variance weighting on log scale will be used to integrate the results and obtain the estimate of the overall odds ratio, 95% confidence interval and p-value for entire study population.

4. Clinical Outcomes

Claims data (ICD-10-CM codes used for defining these outcomes are listed in Appendix C) will be used to define the following clinical outcomes:

- Hospitalization for ischemic stroke or unknown stroke
- Hospitalization for TIA
- Hospitalization for systemic embolism
- Hospitalization for ischemic stroke, TIA or systemic embolism
- Hospitalization for hemorrhagic stroke
- Hospitalization for any bleeding
- Hospitalization for ischemic or hemorrhagic stroke
- Hospitalization for ischemic or hemorrhagic stroke or systemic embolism
- Composite of ischemic stroke, hemorrhagic stroke, and hospitalization for any bleeding
- All-cause in-hospital death

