For each of these outcomes, time-to-event survival methodology will be implemented. Kaplan-Meier estimator¹² will be used to estimate the cumulative incidence rate during all follow-up and the log-rank test¹³ will be used to compare the survival curves. The Cox proportional hazards model with early intervention vs. delayed intervention as main effect will be used to model the time to event, after adjusting for baseline risk factors listed in Appendix A Table A. The hazard ratio, 95% CI and p-value will be presented to summarize the difference in the risk of clinical outcome between early intervention and delayed intervention groups. In-hospital death or medically attended death will be collected through claims data.

Each Data Partner will run SAS program(s) distributed by HPHCI, developed with the statistical team at Duke DCC, to perform analysis on their cohort of patients and return the results to HPHCI. For the comparison of cumulative incidence, each Data Partner will return the estimate of cumulative

occurrence and 95% CI by early intervention vs. delayed intervention, and p-value, as shown in Table 7 in Appendix A (there will be one for each Data Partner). For the comparison of risk, each Data Partner will return the parameter estimate (SE), hazard ratio, 95% CI and p-value, as shown in in Appendix A Table 8 (there will be one for each Data Partner). The statistical team will use meta-analysis methods to integrate the results and obtain the results for entire study population.

5. Health Care Utilization

The total counts of health care utilization (number of outpatient visits, emergency department visits, hospital admissions, and days hospitalized) at the end of follow-up time, including AF and non-AF related care, will be summarized by early intervention and delayed intervention group, as shown in Table 9 in Appendix A.

III. REFERENCES

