History of peripheral vascular disease?					
N					
Yes, %					
History of prior cerebrovascular disease?					
N					
Yes, %					

	Overall (N=XXXX)	Early intervention (N=XXXX)	Delayed intervention (N=XXXX)	p-value	Stand. mean difference (%)
History of heart failure?					
N					
Yes, %					
History of kidney disease?					
N					
Yes, %					
History of MI					
N					
Yes, %					
History of CABG					
N					
Yes, %					
History of coronary stent					
N					
Yes, %					
CHA ₂ DS ₂ VASc score					
N					
Mean (SD)					
Median (25th, 75th)					
0, %					
1, %					
2, %					
3, %					
4, %					
5, %					
6, %					
7, %					
8, %					
9, %					
Bleeding risk score: ATRIA score					
Low (≤ 3), %					
Intermediate (4), %					
High (≥ 5), %					
Hospitalization in the prior 6 months					
0, %					
1, %					
2, %					
≥ 3 , %					
Mean (SD) follow up time					
Minimum follow up time					
Maximum follow up time					
Median follow up time (range across sites)					

For Tables 2 through 9: The SAP workplan(s) run at each Data Partner sites will generate Partner-specific tables of events (per outcome, for early vs delayed intervention) and unadjusted and adjusted model results. These will be returned to the coordinating center; results will be aggregated and meta-analyses will be run on site-specific models to generate final aggregated results.

Table 2a. Odds ratio of filling at least one OAC dispensing or 4 or more INRs (primary endpoint) over the course of the 12-months of follow-up: early intervention vs. delayed intervention in the modified intention to treat (mITT) analysis

	Early Intervention, n/N (%)	Delayed Intervention, n/N (%)	Unadj. Parameter Estimate (SE)	Unadj. Odd Ratio (95% CI)	Adj. Parameter Estimate (SE)	Adj. Odds Ratio (95% CI)	p-value for adjusted OR
OAC dispensing or ≥ 4 INRs at 365 days							
No. who met endpoint due to OAC							
No. who met endpoint due to 4 INRs							
No. who met endpoint due to other code							
No. who met due to 4 INR test PX codes (CPT)							

Table 2b. Odds ratio of filling at least one OAC dispensing or 4 or more INRs (primary endpoint) by varying windows of time (42, 90, and 183 days): early intervention vs. delayed intervention in the modified intention to treat (mITT) analysis

	Early Intervention, n/N (%)	Delayed Intervention, n/N (%)	Unadj. Parameter Estimate (SE)	Unadj. Odd Ratio (95% CI)	Adj. Parameter Estimate (SE)	Adj. Odds Ratio (95% CI)	p-value for adjusted OR

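### Beyond the 365-day primary test, the SAP lets any secondary, clinical or early-window p<0.05 be called statistically significant, with no multiplicity adjustment and no nominal label

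*SAP*

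**What the plan says.** SAP Section II (Statistical Analysis) gives the rule for the whole plan: "All tests will be two-sided and a p-value of <0.05 will be considered statistically significant. No multiplicity adjustment will be made".

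The SAP limits interpretation in two places only. Section I.C treats the 24-month reassessment as exploratory, and Section I.B makes the split by warfarin and novel OAC descriptive, without formal testing. The other 12-month analyses carry no such limit:

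- Section II.D.3, on a secondary endpoint, says that the "p-value will be presented to show whether there is a statistically significant difference in the proportion of patients who are actively on OAC".
- Section II.D.4 lists ten clinical outcomes and says "For each of these outcomes, time-to-event survival methodology will be implemented". Each gets a log-rank test and an adjusted Cox model. Tables 7 and 8 each have 19 rows: nine using the principal discharge diagnosis, nine ignoring that flag, and in-hospital death.
- Table 2b gives adjusted odds ratios and p-values for the "primary endpoint) by varying windows of time (42, 90, and 183 days").
- Section I.G.2 singles out stroke or TIA as an important secondary outcome: "A study with approximately 80,000 patients could provide reasonable power for stroke or TIA outcome under certain assumptions listed below". It states power at a two-sided 0.05 but gives the outcome no place in a testing order.

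**The concern.** Leaving secondary p-values unadjusted is defensible when they are presented as nominal. Here the same paragraph that declines adjustment also calls each p<0.05 statistically significant, and Section II.D.3 repeats that language for a secondary endpoint. A report that follows the SAP to the letter could therefore announce that a mailing changed stroke, bleeding or in-hospital death on one unadjusted p-value among many. It could also announce a significant effect on OAC initiation at 42 days although the 12-month result was null. The stake is what the trial may claim beyond its primary result. The primary result itself is not in question.

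**Working it through.** **1. The plan's own figures.** SAP Section I.G.1 states a "Two-sided type I error rate of 0.05", a "33% OAC initiation rate in the delayed intervention arm", 38% in the early arm and 30% attrition. The continuity-corrected two-proportion formula gives 1963, 2418 and 3401 per arm for 90%, 95% and 99% power. Dividing by 0.70 gives 2805, 3455 and 4859, so totals of 5610, 6910 and 9718, as stated.

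For stroke or TIA, 40,000 × 0.70 = 28,000 per arm:

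- Control rate: 0.33 × 7% + 0.67 × 18% = 14.37%.
- Early arm at 38% initiation: 0.38 × 7% + 0.62 × 18% = 13.82%; power 46.4% (stated 46%).
- Early arm at 40.5% initiation: 0.405 × 7% + 0.595 × 18% = 13.545%; power 80.4% (stated 80%).

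Each of these calculations spends the full 0.05 on a single test.

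**2. Number of clinical tests.** Tables 7 and 8 test the same outcomes, so they are counted once. Principal-diagnosis rows plus in-hospital death: 9 + 1 = 10. With the rows that ignore the flag: 9 + 9 + 1 = 19. The footnote to Table 8 restricts its endpoints to principal diagnoses although the table prints the second block, so the smaller family is the safer basis.

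**3. Simple bounds, no true effect.** For k independent tests the chance of at least one p<0.05 is 1 − 0.95^k: 0.401 for k = 10 and 0.623 for k = 19. These are upper references, because the outcomes overlap. Simulating ten equally correlated test statistics gives 0.35, 0.29, 0.21 and 0.13 at correlations 0.3, 0.5, 0.7 and 0.9.

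**4. Simulation that respects the overlap.** Component events are drawn as Poisson counts with 28,000 patients per arm and equal rates in both arms. Composites are sums of their components. Events in any diagnosis position are the principal-diagnosis events plus 30% to 100% more. Each row is tested with z = (a − b)/√(a + b), where a and b are the two arms' counts. The documents give no rates for these components, so the rates are assumptions: 1% to 4% a year for ischemic stroke, 2% to 3% for bleeding, 2% to 3% for in-hospital death.

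| Event, with no true effect | Chance |
|---|---|
| At least one p<0.05, ten rows | about 0.30 |
| At least one p<0.05, 19 rows | 0.38 to 0.43 |
| False benefit on a stroke-type principal-diagnosis row | about 0.09 (up to 0.11, depending on the rows counted) |
| The same for one prespecified row | 0.025 |

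SAP Appendix C puts the TIA codes (G45.x) inside the ischemic stroke definition. Building that in lowers the first two figures only to 0.27–0.28 and 0.37–0.40.

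**5. Early windows of the primary endpoint.** Assume a constant hazard reaching 33% at one year, h = −ln(0.67)/365. The cumulative proportions at 42, 90, 183 and 365 days are 0.045, 0.094, 0.182 and 0.330. For nested indicators with p1 < p2, the correlation is √[p1(1 − p2)/(p2(1 − p1))], which ranges from 0.31 (42 with 365 days) to 0.68 (90 with 183 days). Simulating the four statistics gives:

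- any of the three early windows significant: 0.116;
- an early window significant and the 365-day result not: 0.097;
- the same, with the early result favoring the intervention: 0.049.

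**The case against.** The strongest defense is that the trial has one primary endpoint and one primary analysis, that endpoints are ranked as primary, secondary and exploratory, and that the lack of adjustment is openly declared. Unadjusted secondaries after a single primary are common. The SAP already plans effect estimates with 95% CIs for its modeled endpoints. Its CONSORT worksheet (Appendix B) also asks the report to separate prespecified from exploratory analyses and to discuss multiplicity. All of this is true, and it rules out any claim that the main inference is damaged. It does not close the gap. A reporting checklist does not alter a rule that calls each p<0.05 significant, and disclosing that there is no adjustment does not tell the reader to treat the p-values as nominal.

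Three stronger readings are tempting, and the documents do not support them.

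- **Every window is a primary analysis.** Section II.C refers to the "arms using the data shown in Tables 2a-c. The adjusted analysis will be considered the primary analysis". In context that sentence chooses adjusted over unadjusted analysis. Sections II.C.1 and II.C.2 define the endpoint over the full follow-up, and the main row of Table 2a is at 365 days. Table 2b needs a label, but day 42 is not made primary.
- **Early windows yield false claims at several times 0.05.** A figure of 0.147 arises if all four windows are counted, but that includes the legitimate 365-day test. The event that matters has a chance of 0.097.
- **The 19-row family sets the size of the problem.** The Table 8 footnote contradicts the block that would make up that family.

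**Conclusion.** The concern holds as a gap in interpretation. The 365-day primary test stays at 5%. What is missing is a limit on the words statistically significant for the other 12-month analyses. About 0.30 for the ten clinical rows rests on assumed event rates and on independence between the component events. The early-window figure of about 0.10 rests on a constant initiation hazard. Even ten tests correlated at 0.9 give 0.13, so the direction does not depend on those choices. This is a cheap improvement worth making, not a defect that threatens the trial's main result.

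**What to change.** In SAP Section II, replace the significance sentences with wording such as: *The two-sided 0.05 criterion applies to one test, the adjusted pooled mITT odds ratio at 365 days (Table 2a, first row). All other p-values are nominal, are not adjusted for multiplicity and will not be described as statistically significant; estimates with 95% CIs will be reported.* Label Table 2b secondary and descriptive. In Section II.D.3, delete the clause that gives demonstrating significance as the purpose of the p-value. Keep bleeding and in-hospital death reported with 95% CIs so that a harm signal stays visible.

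The cost is a few sentences and table footnotes before database lock, with no new data. The shells of Tables 5 and 9 show a p-value but no interval for the comparison between arms, so an interval there would be a small addition to the output. The downside is that an isolated secondary p<0.05 can no longer be called statistically significant.

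Neither an alpha adjustment nor a testing sequence is asked for. Bonferroni over ten outcomes (0.005 each) would cut stroke or TIA power from 80.4% to 50.4% at the larger effect and from 46.4% to 17.4% at the smaller. A sequence starting with stroke or TIA could not be run as the SAP stands: that outcome is not defined in Section II.D.4 or Table 8, and Appendix C places the TIA codes within ischemic stroke. Whether to gate at all is a trade-off for the sponsor.

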Baseline characteristics of the early intervention and delayed intervention cohorts will be based on the claims data at the time of randomization (among those eligible for inclusion in the analysis). Frequency distribution and summary statistics for demographic and baseline variables will be presented by early intervention group, delayed intervention group, and for the overall study population (Tables 1 and 1S in Appendix A). Key demographic and baseline variables to be summarized include: geographic region, age, sex, risk factors for stroke, risk factors for bleeding, and selected comorbid conditions. Depending on the data availability and effort required by Data Partners, a sensitivity analysis may be conducted to examine the number of patients associated with different provider types (examination of outcomes by provider type may also be considered). Categorical variables will be presented as frequencies (percentages) and will be compared between groups by using Pearson's chi-square or Fisher's exact test if the count in any cell is less than 5. Continuous variables will be summarized as mean (\pm SD) and median (25th, 75th percentiles); the comparison between the two groups will be conducted using Wilcoxon rank-sum test for the data within each Data Partner. For the continuous variables in combined study population, only the mean will be summarized. Standardized mean differences will also be reported.

For continuous variables, the standardized mean difference (%) is defined as

$$d = \frac{100 \times (\bar{x}_T - \bar{x}_C)}{\sqrt{\frac{S_T^2 + S_C^2}{2}}}$$

Where \bar{x}_T and \bar{x}_C denote the sample mean of a baseline variable in early intervention group and delayed intervention group, respectively. s_T^2 and s_C^2 denote the sample variances for each group.

For binary categorical baseline variables, the standardized mean difference (%) is defined as

$$d = \frac{100 \times (p_T - p_C)}{\sqrt{\frac{p_T(1 - p_T) + p_C(1 - p_C)}{2}}}$$

Where p_T and p_C denote the proportion of binary variables in early intervention group and delayed intervention group, respectively.

For categorical variables with multiple levels of values such as variable Region in Table 1 and 1S, a multivariate Mahalanobis distance method to generalize the standardized mean difference which is defined as

$$d = 100 \times \sqrt{(T - C)'S^{-1}(T - C)}$$

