For all tables below, the study coordinating center at HPHCI will receive Data Partner-specific tables (there will be one of each table per Data Partner). The coordinating center will generate aggregated tables for Data Partners (shown below), these will be shared with the Duke DCC statistical team. Duke DCC will have a data-use agreement with each Data Partner as necessary in order to receive/access aggregate summary data, which are housed at HPHCI. Duke DCC will conduct the meta-analysis across all study sites. No Data Partner-specific tables will be shared beyond the coordinating center and Duke DCC, if agreed upon by Data Partners, the analytic team; only data aggregated across sites will be published or made public.

Table A. Baseline covariates to be adjusted in the models described in sections II.C, II.D.1, II.D.2, II.D.3, and II.D.4

Demographics
Age (restricted cubic spline terms)
Sex (male vs. female)
Medical history
History of anemia (yes vs. no)
History of hypertension (yes vs. no)
History of diabetes (yes vs. no)
History of hospitalization for any bleeding (yes vs. no)
History of peripheral vascular disease (yes vs. no)
History of prior cerebrovascular disease (yes vs. no)
History of heart failure (yes vs. no)
History of kidney disease (yes vs. no)
History of MI
History of CABG
History of coronary stent
Bleeding risk score: ATRIA score (Low (≤ 3) vs. Intermediate (4) vs. High (≥ 5))
Hospitalization in the prior 6 months (0 vs. 1 vs. 2 vs. ≥ 3)

Table 1. Baseline characteristics of all patients in the modified intention to treat (mITT) analysis by early intervention vs. delayed intervention

	Overall (N=XXXX)	Early intervention (N=XXXX)	Delayed intervention (N=XXXX)	p- value	Stand. mean difference (%)
Demographics					
Age					
N					
Mean (SD)					
Median (Min, 25 th , 75 th , Max)					

	Overall (N=XXXX)	Early intervention (N=XXXX)	Delayed intervention (N=XXXX)	p-value	Stand. mean difference (%)
30-34 yr, %					
35-39, %					
40-44, %					
45-49, %					
50-54, %					
55-59, %					
60-64, %					
65-69, %					
70-74, %					
75-79, %					
≥ 80, %					
Sex					
N					
Female, %					
Region					
New England, %					
Mid-Atlantic, %					
South-Atlantic, %					
Midwest, %					
Mountain, %					
Pacific, %					
Unknown, %					
Medical history					
History of anemia?					
N					
Yes, %					
History of hypertension?					
N					
Yes, %					
History of diabetes?					
N					
Yes, %					
History of hospitalization for any bleeding?					
N					
Yes, %					

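### As printed, the SAP's multi-level standardized difference has the wrong sign on the off-diagonal covariances, so following it would misstate baseline balance for variables with three or more levels

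*SAP*

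**What the plan says.** SAP section II.B, Demographics and Baseline Characteristics, gives three formulas for the standardized mean difference: one for continuous variables, one for binary variables, and one introduced by "For categorical variables with multiple levels of values such as variable Region in Table 1 and 1S". The third is described as "a multivariate Mahalanobis distance method to generalize the standardized mean difference": d = 100 x sqrt((T-C)'S^-1(T-C)). T and C hold the early-arm and delayed-arm proportions for categories 2 onward, so category 1 is left out as the reference.

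S is called a "covariance matrix define as" two expressions. Each diagonal element is half of "p_{1k}(1 - p_{1k}) + p_{2k}(1 - p_{2k", with the brackets closed. Each off-diagonal element is half of "p_{1k}p_{1l} + p_{2k}p_{2l", again with the brackets closed and with no minus sign in front.

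The section also states: "Aggregate standardized mean differences will be calculated based on aggregated frequencies, mean, and standard deviations". The same SAS program runs at every Data Partner and the table is then produced for the whole study. Nothing elsewhere in the SAP or protocol corrects the sign or says which level of a variable is category 1.

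**The concern.** A Mahalanobis distance needs the covariance matrix of the category indicators. The printed diagonal is right: it is the multinomial variance p(1-p), averaged over the two arms. The printed off-diagonal has the right size but the opposite sign. A patient in one region cannot be in another, so the two indicators are negatively correlated and their covariance is -p_k p_l.

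The sign matters in two ways. The value of d is wrong in general, and can be too high or too low. It also loses a property that the correct form has, namely that it does not depend on which category is left out.

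What is at stake is a descriptive measure, but one with some use here. The modified intention-to-treat analysis in SAP section II removes patients after randomization, and the SAP concedes that address validity was not assessed in the delayed arm. Tables 1 and 1S are where a reader would look for any resulting imbalance. With about 80,000 patients planned, a p-value can flag trivial differences, so the standardized difference is the more informative measure of size. Region is not among the Table A adjustment covariates. The ATRIA class and the number of hospitalizations in the prior six months are also multi-level rows of Tables 1 and 1S that the formula would cover, although both of these are in Table A.

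**Working it through.** **Inputs.** The formulas for d and S come from SAP section II.B. Region has seven levels in the Table 1 shell (New England, Mid-Atlantic, "South-Atlantic", Midwest, Mountain, Pacific, Unknown). The tables are empty shells, with column heads such as "Overall (N=XXXX", so no standardized difference exists to reproduce. All proportions below are assumptions chosen for illustration.

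**Sign of the covariance.** For indicators X_k and X_l of two different categories of one variable, the product X_k X_l is always 0. So Cov(X_k, X_l) = E(X_k X_l) - p_k p_l = 0 - p_k p_l. A simulation of 1,000,000 draws with proportions 0.5, 0.3, 0.2 gave -0.150, -0.100 and -0.060, matching -0.5 x 0.3, -0.5 x 0.2 and -0.3 x 0.2.

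**Three-level example, by hand.** Early 0.50/0.30/0.20, delayed 0.40/0.35/0.25.

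Leaving out category 1:
- T - C = (-0.05, -0.05)
- S_11 = (0.21 + 0.2275)/2 = 0.21875
- S_22 = (0.16 + 0.1875)/2 = 0.17375
- size of S_12 = (0.06 + 0.0875)/2 = 0.07375
- determinant (same for either sign) = 0.21875 x 0.17375 - 0.07375^2 = 0.03256875
- d^2 (before the factor of 100) = 0.0025 x (S_11 + S_22 - 2 S_12) / determinant
- Minus sign: 0.0025 x (0.3925 + 0.1475)/0.03256875 = 0.04145, so d = 20.36%
- Plus sign, as printed: 0.0025 x (0.3925 - 0.1475)/0.03256875 = 0.01881, so d = 13.71%

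Leaving out category 3 instead:
- T - C = (0.10, -0.05)
- S_11 = 0.245, S_22 = 0.21875, size of S_12 = 0.145, determinant again 0.03256875
- d^2 = (0.01 x 0.21875 + 0.01 x S_12 + 0.0025 x 0.245)/determinant
- Minus sign: 0.00135/0.03256875 = 0.04145, so d = 20.36%, unchanged
- Plus sign: 0.00425/0.03256875 = 0.1305, so d = 36.12%

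Leaving out category 2, the printed form gives 32.07% and the minus sign again gives 20.36%.

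**Other assumed mixes**, with each level left out in turn:

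| Early vs delayed (%) | Minus sign, every reference | As printed, range over references | As printed, first level left out |
|---|---|---|---|
| 40/20/10/10/10/5/5 vs 34/21/11/11/11/6/6 | 12.95% | 7.30% to 18.98% | 7.30% |
| 10/15/25/20/10/15/5 vs 15/15/20/20/10/15/5 | 17.71% | 12.95% to 21.60% | 12.95% |
| 90/4/3/1/1/0.5/0.5 vs 89/4.5/3.2/1.2/1.1/0.5/0.5 | 3.59% | 3.39% to 14.72% | 3.39% |
| 70/10/20 vs 68/11/21 (three levels, as for ATRIA class) | 4.50% | 3.80% to 9.82% | 3.80% |

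**Typical size.** In 5,000 random seven-category sets, the ratio of printed to correct d had a median of 1.16 (95% range 0.71 to 1.40). The largest over the smallest printed d across references had a median of 1.45 (95% range 1.19 to 2.37); for the corrected form this ratio was 1.000. The printed d^2 was never negative in these sets, so a program coded from it would not fail visibly.

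**Control.** With two categories there is no off-diagonal term, and both signs give the same value (6.05% for 45/55 against 42/58).

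**Chance imbalance only.** With an assumed 20,000 per arm and one seven-region mix (10/15/25/25/10/10/5%), the correct d had a median of 2.3% (95% range 1.2% to 3.8%). The printed d had a median of 2.5% (1.2% to 4.3%), with a maximum of 6.2% over all references.

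**The case against.** The strongest objection is about provenance. The whole point is one leading minus sign in a machine-read formula. The minus signs inside (1 - p) survived, but a lone minus at the start of a row is easier to lose. The SAP names a Mahalanobis distance and a covariance matrix, so the intended sign is presumably negative. This stands: the documents available cannot show whether the SAP itself carries the error. The SAP also has the programs validated and beta-tested, and the code may already be right.

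A second objection is that the formula fixes the reference as category 1, so a range over seven references overstates the freedom. This stands in part. The SAP does not say which level is category 1, and fixing it does not cure the error: with the first level left out, the first seven-region example gives 7.30% where 12.95% is correct.

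A third is that the illustrative imbalances are unrealistic for a trial randomized 1:1 within each plan. This also stands. At an assumed 20,000 per arm, the two larger seven-region examples would give chi-square p-values of about 1e-33 and 1e-64. Under chance imbalance alone both versions stay small. Material distortion in balanced arms needs one category to dominate, as could happen within a single Data Partner.

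A reader might infer that the trial's reported regional balance is wrong, or that its effect estimates are compromised. The documents support neither. No balance figure exists yet. The logistic and Cox models adjust for a fixed list whatever the observed balance. The SAP ties no threshold or action to the standardized difference, and Table 1 also shows region percentages by arm with a p-value that does not use S.

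**Conclusion.** The formula as printed is wrong for what the SAP says it is. If followed, it would misstate the standardized difference for every variable with three or more levels handled this way, in either direction, and the value would depend on an unstated coding choice. In the assumed examples the printed value runs from about 0.56 times the correct one (7.30/12.95) to about 4.1 times (14.72/3.59); the upper figure arises where one region holds about 90% of patients and a small region is left out. These sizes rest on invented proportions. The sign error and the dependence on the reference follow from the algebra and do not.

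The consequence is minor. It is limited to the standardized-difference column of Tables 1 and 1S for multi-level variables. Continuous and binary standardized differences, the p-values in those tables, and all endpoint analyses are untouched. Confidence that the error is in the SAP itself is medium, because a sign lost in text extraction cannot be excluded.

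**What to change.** First check the source PDF of SAP section II.B and the SAS program distributed to the Data Partners. If the minus sign is absent from either, set S_kl = -(p1k*p1l + p2k*p2l)/2 for k not equal to l. State in the SAP which level of each variable is category 1. Add one validation test to the program: drop each level in turn and confirm that d does not change, for Region, ATRIA class, prior hospitalizations and any other variable with three or more levels that uses this formula. The cost is one sign in the SAP, one in the code if needed, and a short test. No additional data are needed from the Data Partners, since d is computed from the category proportions that the tables already report.
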